10.4.4 Analysis of the Secondary Endpoint(s)

Wilcoxon signed-rank tests will be used to assess paired pre- and post-BCI peripheral blood measurements, and to assess paired post-BCI peripheral blood CD8⁺ T cell responses and T cell PD-1 expression in BAL effluent.

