| Brief Summary | This is a first-in-human, safety and feasibility study of bronchoscopic cryo- immunotherapy (BCI) of peripheral lung tumors in advanced non-small cell lung cancer (NSCLC) and suspected NSCLC. BCI has the potential to stimulate anti-tumor immune responses. Pre- and post-BCI peripheral blood samples will be analyzed to assess for anti-tumor immune responses. Post- BCI peripheral blood will be collected 7 and 14 days after the procedure. Additionally, pre-BCI bronchoalveolar lavage (BAL) specimens will be collected to correlate PD-1 phenotype on pre-BCI BAL lymphocytes by single cell RNA sequencing and BCI-induced anti-tumor immune responses. | | |
| Phase | Phase I | | |
| Objectives Primary: • Establish safety and feasibility of BCI and determine the maximu tolerated dose (MTD) (i.e., freeze duration) Secondary: | | | |
| Assess the extent of BCI-induced anti-tumor immune respons | | | |
| Methodology Dose-escalation trial using a 3+3 design Primary: Feasibility and Safety | | | |
| | Feasibility: successful performance of BCI in at least 80% of participants in whom BCI is attempted Safety endpoints: Dose-limiting toxicity (DLT), defined as incidence of bleeding complications and pneumothorax, length of time to perform BCI, length of fluoroscopy exposure during BCI, and other adverse events | | |
| Endpoints | Secondary: Immune Analysis and Tumor Response Changes in peripheral blood CD8⁺ T cells expressing a combination of Ki67⁺,PD-1+, HLA-DR⁺, CD38⁺, and Bcl-2^{low} after BCI Changes in peripheral blood lymphocyte gene expression after BCI, which will be assessed by the PanCancer OncolmmuneTM profile panel, a 770-plex gene expression panel covering innate and adaptive immune responses (NanoString® Technology, Seattle, WA) Correlation of PD-1 phenotype of pre-BCI BAL lymphocytes by single-cell RNA sequencing and BCI-induced anti-tumor immune responses. | | |
| Study Duration 12 months | | | |
| Participant Duration | 14 days | | |
| Duration of IP administration | BCI will be performed once at the time of a standard-of-care bronchoscopy for another indication. BCI is anticipated to take approximately 15-25 minutes. | | |

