3.1 Primary Objective: Demonstrate Feasibility and Determine the MTD

1) Demonstrate feasibility of BCI

We hypothesize that BCI will be feasible, defined as successful performance in at least 80% of patients in whom BCI is attempted. Successful performance of BCI will require identification of the target peripheral lung tumor by radial endobronchial ultrasound within 20 minutes followed by completed cryoablation of target tumor.

2) Determine the safety and MTD of BCI

We hypothesize that BCI will prove safe at each planned dose level. Using a standard 3+3 design, the trial will determine the maximally tolerated dose (MTD) by sequentially assessing increasing freeze times during the procedure. Dose-limiting toxicity (DLT) is defined as the occurrence of any of the following: grade 2 or 3 bleeding, pneumothorax necessitating tube thoracostomy, or any NCI CTCAE grade 4 or 5 adverse events, which may be possibly, probably, or definitely related to BCI (33). The monitoring period for dose limiting toxicity will be for seven days post-BCI.

3.2 Secondary Objectives: Assess BCI Induced Anti-Tumor Immune Responses1) Pre- and Post-BCI Peripheral Blood Analysis

We hypothesize that BCI will induce activation and proliferation of peripheral blood T cells. Based on previous work (26, 27) (see section 2.1.IV for full details), we hypothesize that some combination of the following markers will be displayed on peripheral blood CD8⁺ T cells after BCI: HLA-DR and CD38 (surface markers of CD8⁺ T cell activation), Ki-67 (a cell cycle marker of proliferation), Bcl-2 (an anti-apoptotic protein downregulated on activated CD8⁺ T cells), and PD-1. We also hypothesize that there will be significant changes in peripheral blood lymphocyte gene expression after BCI, which will be assessed by the PanCancer OncoImmune[™] profile panel, a 770-plex gene expression panel covering innate and adaptive immune responses (NanoString® Technology, Seattle, WA).

2) Investigate BCI Association with PD-1 Phenotype of Effector T cells in NSCLC

We hypothesize that BCI will induce PD-1 phenotype in circulating effector T cells on single-cell RNA sequence analysis and that CD8+ T cell responses to BCI will be greater among subjects with high PD1 expressing T cells in BAL effluent.

4 Study Design and Endpoints

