4.2.2 Secondary Study Endpoints: Immune Analysis

CONFIDENTIAL

1) Assess BCI Induced Anti-Tumor Immune Responses in Peripheral Blood

Research Samples: Peripheral blood will be collected by the investigatory team prior to BCI on the day of procedure, and at approximately 7 days and 14 days after BCI (± 3 days). Specimens may be processed in the [name] Environmental Lung Disease Laboratory, the [name] Translational Lung Biology Laboratory, or in the [name] Laboratory on the campus of the New York University Langone Medical Center/Bellevue Hospital Center.

Flow cytometry: Peripheral blood samples will undergo Ficoll-Paque separation. The buffy coat containing peripheral blood mononuclear cells (PBMCs) will be isolated, and then washed with phosphate buffered saline. Isolated PBMC will undergo staining with antibodies against the markers described in Table 1 (Section 2.1: Background Information and Relevant Literature – Subsection VI Biomarkers to Assess for BCI Induced Anti-Tumor Immune Response) in [name] laboratory in the Perlmutter Cancer Center at NYU School of Medicine.

Data will be acquired on a BD Symphony A5 flow cytometer, and analyzed using FlowJo software and various R-based bioinformatics algorithms developed previously by [name] and colleagues. The 30-parameter flow cytometry panels we plan to use (Table 1) will query multiple markers of activated cells (including a broad range of cytokines), and multiple markers associated with immune checkpoints (along with markers of T-cell differentiation). To ensure that our results do not reflect global T-cell activation or exhaustion, in follow-up experiments, we will substitute a cocktail of peptide MHC Class I multimers ("tetramers") against influenza and EBV responses into panel 1 (the cocktail will cover various epitopes and HLA-types) and stimulate a parallel aliquot of cells from panel 2 with a CEF (CMV/EBV/influenza) cocktail of peptides or the same tetramer cocktail used for Panel 1.

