mRNA analysis: We will also be assessing a variety of other immune biomarkers from peripheral blood utilizing the NanoString[™] platform, including cytokine gene expression, that may allow for the establishment of a variety of peripheral blood biomarkers to correlate with the effects of BCI in advanced NSCLC. Once sorted, the CD8+ and CD4+CD25- cells (non-Treg cells) will be processed for RNA extraction and NanoString[™] mRNA quantitation. RNA extraction will be performed using the MARIS technique to insure RNA quality after sorting (35). We are particularly interested in determining gene expression of proteins involved in T cell activation and immune regulation, such as CTLA-4, PD-1, OX-40, TIM-3, IL-10, TGF-ß, IL-2, MHC-II and TNF-α. The transcriptome data will be processed in collaboration with the Biostatistics Division led by [name] at the NYU School of Medicine to calculate the relative expression of the key genes of interest previously noted. The NanoString[™] platform offers the convenience of straightforward high-throughput mRNA quantitation using RNA barcodes to probe and count mRNA transcripts of interest (28). Our preliminary analysis will be conducted with the pre-designed Oncolmmune[™] Profile panel, which measures 770 gene targets most relevant in tumor immunobiology.

2) Investigate BCI Association with PD1 phenotype of Effector T cells in NSCLC

Research Samples: In addition to peripheral blood specimens as described previously, BAL fluid will be collected from regions of the primary tumor and of the distal portion of the same lung.

Using a subset of samples from enrolled subjects enrolled with sufficient BAL specimens, we will perform single-cell RNA sequencing on sorted CD3+ T cells from BAL and PBMCs obtained at the time of BCI. This approach will be repeated in PBMC after 7 and 14 days post BCI. The percentage of PD-1 expressing T lymphocytes will be determined in CD4⁺ and CD8⁺ cells from both BAL and PBMC compartments. PD1⁺ cell percentage and transcriptome will be compared between responder categories. RNA sequencing and subsequent data analysis will be performed in the Genomic Technology and Bioinformatics Cores of NYU School of Medicine.

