10.1 Statistical and Analytical Plans

All dose-limiting toxicities will be tabulated by type of DLT and dose level.

In addition to tabulating toxicities, we will record data on pre- and post-BCI peripheral blood biomarkers. For the continuous immunologic outcomes, we will calculate means by sampling time and perform exploratory graphical analyses, but with the small sample sizes and potentially irregular lengths of the series of observations it will not be possible to perform formal longitudinal analysis. We will apply non-parametric tests to evaluate changes in immunologic outcomes before and after BCI. Details are provided below.

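### The 770-gene panel falls by default to uncorrected signed-rank tests; once false discoveries are controlled, that test can find little if usable pairs drop to about 12 or fewer, and a moderated paired model would do better

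*Combined protocol and SAP*

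**What the plan says.** The Endpoints row of the Protocol Summary lists change in lymphocyte gene expression as a secondary endpoint, measured with "a 770-plex gene expression panel covering innate and adaptive immune responses". Section 3.2 states the hypothesis: "We also hypothesize that there will be significant changes in peripheral blood lymphocyte gene expression after BCI". Section 4.2.2 says that "the CD8+ and CD4+CD25- cells (non-Treg cells) will be processed for RNA extraction", and that the panel is the one "which measures 770 gene targets most relevant in tumor immunobiology". Blood is drawn before BCI and at about day 7 and day 14.

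On analysis, 10.1 says "We will apply non-parametric tests to evaluate changes in immunologic outcomes before and after BCI", and 10.4.4 says "Wilcoxon signed-rank tests will be used to assess paired pre- and post-BCI peripheral blood measurements". No section gives the panel a different method. Section 10.4.1 sets significance at 0.05 and states no multiplicity or false-discovery rule. It also says that the secondary outcomes are not powered.

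**The concern.** A signed-rank test on n pairs cannot give a two-sided exact p-value below 2/2^n. For one or two flow-cytometry markers this is harmless. For 770 genes it matters, because a credible list of changed genes needs p-values well below 0.05, and with few pairs the test may be unable to produce them.

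The plan therefore has two linked gaps. Without a correction, the panel yields a list that may consist largely of chance findings. With a correction but the same test, it may yield nothing even when many genes truly change. Either outcome would waste the panel as a source of leads for the later combination studies that 10.5 says these results should inform. A gene-by-gene rank test also makes no use of the variance information shared across 770 genes, which is valuable when n is small.

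**Working it through.** **Inputs from the protocol.** 770 genes (Protocol Summary, 3.2, 4.2.2); two sorted cell fractions and two post-BCI draws (4.2.2); 0.05 per test (10.4.1); 15 to 24 participants (5.6), aiming for about 24 (10.5). Sidedness is not stated. The gene hypothesis has no direction, so two-sided tests are assumed.

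**The plan's own figure.** Section 10.5 gives 15 subjects for about 80% power at about 0.75 SD with correlation 0.5. The standardised paired difference is 0.75/√(2 × (1 − 0.5)) = 0.75. At n = 15 and two-sided 0.05, power is 0.83 by normal approximation, 0.77 by paired t and 0.75 by exact signed-rank (simulated). The figure is approximately reproduced, for a single marker at 0.05.

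**As written.** If no gene changes, 770 × 0.05 = 38.5 are expected to be called at each comparison, somewhat fewer because the exact test is discrete. Over two fractions and two draws the ceiling is 4 × 38.5 = 154.

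**With a correction.** The floor is 2/2^n. Bonferroni over 770 needs 0.05/770 = 0.000065. Benjamini-Hochberg at 5% needs at least k genes at the floor before it can declare any, with k ≥ floor × 770/0.05.

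| Pairs | Floor | Genes needed at floor | Floor below 0.000065? |
|---|---|---|---|
| 9 | 0.0039 | 61 | no |
| 12 | 0.00049 | 8 | no |
| 14 | 0.00012 | 2 | no |
| 15 | 0.000061 | 1 | yes, just |
| 24 | 0.00000012 | 1 | yes |

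If all 2 × 2 × 770 = 3,080 tests form one family, Bonferroni needs at least 17 pairs.

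**How pairs fall below 15.** Escalation may stop early at an MTD (6.1.2, 8.4). Patients found not to have NSCLC give no post-BCI blood (7.1.2). Samples from participants who withdraw after the post-BCI draws are discarded, and visits can be missed (5.7.2). The documents give no rates for these losses, so the number of pairs is a range, not a forecast.

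**Size of the loss.** Simulated panels of 770 independent genes, 38 of them (5%) truly shifted, normal log differences, gene variances scaled inverse chi-square with 6 df, Benjamini-Hochberg 5%. Effects are in SDs of the paired difference. All of these are assumptions. Share of true genes found:

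| Pairs | Shift | Signed-rank | Moderated paired t |
|---|---|---|---|
| 9 | 1.0 SD | 0% | 12% |
| 12 | 1.0 SD | 3% | 34% |
| 15 | 1.0 SD | 39% | 59% |
| 21 | 1.0 SD | 81% | 88% |
| 24 | 1.0 SD | 90% | 93% |
| 12 | 0.75 SD | 0% | 5% |
| 15 | 0.75 SD | 6% | 14% |

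These carry simulation error of a few points. The realised false discovery rate of the moderated t was close to 5%.

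**Sensitivity.** A separate simulation used a 4-df variance prior and 77 changed genes (10%). With normal data at 1.0 SD, mean true genes found, signed-rank against moderated t, were 16 against 36 at 12 pairs, 46 against 54 at 15 and 69 against 71 at 21. With t-distributed differences on 4 df at 0.75 SD, they were 26 against 28 at 15 pairs, 53 against 50 at 21 and 61 against 57 at 24.

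**The case against.** The strongest reply is that the plan is for 15 to 24 participants. If most of them give pairs, the floor hardly matters: one gene can pass 0.05/770 at 15 pairs, and at 21 to 24 the two methods are close, with the rank test slightly ahead under heavy tails. This stands. A reader might infer that signed-rank tests leave almost no gene detectable anywhere from 9 to 15 pairs. The documents do not support that: 15 is the low end of planned enrolment, and 9 appears nowhere in them.

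Second, the floor binds only after a correction that the plan does not contain. At an uncorrected 0.05 it does not bind from 6 pairs upward. This also stands, so the missing false-discovery rule comes first and the choice of test follows from it.

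Third, gene-by-gene testing is never stated. Section 4.2.2 speaks of using the data "to calculate the relative expression of the key genes of interest previously noted", names nine examples and calls the full-panel run preliminary. For nine genes, 0.05/9 = 0.0056 is reachable even at 9 pairs. But the Protocol Summary and 3.2 make the whole panel a secondary endpoint, and no other analysis of it is offered.

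Fourth, the simulations draw variances from the family that the moderated test assumes, which favours it. Nor is that test a guarantee: with 9 pairs and 15 genes shifted by 1.0 SD, it finds about 0.7 of a gene on average.

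Finally, the plan admits that secondary outcomes are underpowered. That excuses the sample size. It does not excuse a method that draws less from the same samples when pairs are few.

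**Conclusion.** The concern holds in a conditional form. The panel has no stated method other than uncorrected signed-rank tests, which would call up to about 38 of 770 unchanged genes at each comparison. If false discoveries are controlled and usable pairs are about 12 or fewer, the signed-rank floor blocks most discovery, and a moderated paired t finds clearly more: about 34% against 3% at 12 pairs for 1.0 SD shifts. At 15 pairs the advantage is moderate (59% against 39%). At 21 to 24 it is small and can reverse with heavy tails. At the protocol's 0.75 SD the absolute gains are smaller. These sizes rest on assumed effects, number of changed genes, variance prior and independence between genes.

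A reader might also infer that genes tied at the floor cannot be ranked. They can still be ordered by fold change or median paired difference; what is lost is the ability to separate them by p-value.

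The method has to be fixed before the number of pairs is known. The moderated model gains much at low n and loses little at high n, so it is the better default for this secondary endpoint.

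**What to change.** In 10.4.4, take the NanoString panel out of the signed-rank sentence. State that log2 normalised counts will be analysed with a paired linear model (participant as block, draw as factor) and empirical-Bayes moderated t statistics, separately in the CD8+ and CD4+CD25- fractions. Report log2 fold changes with intervals and false-discovery-adjusted p-values, and say which tests form the family: each fraction and draw separately, or all together. Keep the signed-rank test for the flow-cytometry percentages, and as a sensitivity check for the key genes named in 4.2.2. Add to 10.4.1 that the unadjusted 0.05 level does not apply to the panel, and align 10.1.

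The cost is SAP wording and standard software, with no new samples and no change to trial conduct. The downside is that the model assumes approximately normal log2 counts, which residual plots should check.

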10.2 Statistical Hypotheses

- 1) BCI will be feasible and safe, with a maximum tolerated dose to be determined in this trial.
- 2) Post-BCI peripheral blood will demonstrate an increase in the percent of CD8⁺ T cells expressing a combination of Ki67⁺, PD-1+, HLA-DR⁺, CD38⁺, and Bcl-2^{low} compared to pre-BCI peripheral blood CD8⁺ T cells.
- 3) CD8+ T cell responses to BCI will be greater among subjects with high PD-1 expressing T cells in BAL effluent.

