10.4.7 Additional Sub-Group Analyses

Sub-group analyses as described below will employ Wilcoxon signed-rank tests as described above for secondary analyses. In particular:

- 1) We will compare changes in pre- and post BCI peripheral blood CD8⁺ T cells expressing a combination of Ki67⁺,PD-1+, HLA-DR⁺, CD38⁺, and Bcl-2^{low} at each dose level.
- 2) In the subset of participants receiving active treatment (radiation therapy, chemotherapy, and/or immunotherapy in the past 30 days) for non-small cell lung cancer, we will investigate if the combination of cryoablation and his/her current treatment will lead to enhanced increases in the percent of CD8⁺ T cells expressing a combination of Ki67⁺,PD-1+, HLA-DR⁺, CD38⁺, and Bcl-2^{low} compared to participants treated with BCI alone.

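### The Wilcoxon signed-rank test is assigned to the association between BAL PD-1 and CD8 response, which it does not measure, and is the only test named for active treatment versus BCI alone, a contrast between different participants

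*Combined protocol and SAP*

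**What the plan says.** Section 10.4.4 is a single sentence with two uses of one test. It begins "Wilcoxon signed-rank tests will be used to assess paired pre- and post-BCI peripheral blood measurements, and to assess paired post-BCI peripheral blood" and ends, for CD8 cells, "T cell responses and T cell PD-1 expression in BAL effluent". The first use is a pre/post comparison. The second pairs a blood response with a lavage measurement in the same person.

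The question behind the second use is stated in three ways:
- The Protocol Summary lists the endpoint as "Correlation of PD-1 phenotype of pre-BCI BAL lymphocytes by single-cell RNA sequencing and BCI-induced anti-tumor immune responses".
- Hypothesis 3 in Section 10.2 says that CD8 "T cell responses to BCI will be greater among subjects with high PD-1 expressing T cells in BAL effluent", and Section 3.2 says the same. No cut-off for high is given.
- Section 4.2.2 plans to compare PD-1+ percentage and transcriptome between responder categories. It does not define a responder or name a test, and it expects only a subset of participants to have enough BAL material.

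Section 10.4.7 opens with "Sub-group analyses as described below will employ Wilcoxon signed-rank tests as described above for secondary analyses". Its item 2 begins "In the subset of participants receiving active treatment", defined by therapy in the past 30 days, and asks whether their increases are enhanced "compared to participants treated with BCI alone".

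Section 10.1 promises non-parametric tests of before/after change and defers the details to these sections. No rank correlation, rank-sum or other between-group test is named anywhere.

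**The concern.** A signed-rank test takes one difference per person and asks whether those differences are centred on zero. That suits blood before and after BCI, where both values are the same measurement. For CD8 response and BAL PD-1 the difference subtracts one quantity from another, and its centre shows how far apart the two sit. It does not show whether people with higher PD-1 respond more. Followed literally, the plan would attach a p-value at the 0.05 threshold of Section 10.4.1 to hypothesis 3 that answers a different question.

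In Section 10.4.7 item 2 the two groups are disjoint. Each person has a pre/post pair, but nobody in one group is paired with anybody in the other. The test described can be run within each group, and neither result tests whether one increase exceeds the other. Left open, the test, the cut-off for high PD-1 and the post-BCI day could all be chosen after the data are seen.

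**Working it through.** **The plan's own figure.** Section 10.5 gives 15 subjects, about 80% power, a difference of about 0.75 SD and a within-subject correlation of 0.5. The SD of the change is √(2(1−0.5)) = 1.0 SD. With two-sided 0.05 (the plan does not state sidedness), the normal approximation gives 0.75×√15 − 1.960 = 0.945, which is 82.8% power. The paired t test gives 77.1%. The two bracket 80%, so the figure is reproduced as an approximation. It covers pre/post blood only. No figure is given for the BAL association or the treatment contrast.

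**What signed-rank responds to.** Put both measures on a scale with SD 1, with a gap g between their centres and correlation ρ. The within-person difference has mean g and SD √(2(1−ρ)), so the test is driven by g/√(2(1−ρ)):
- ρ=0.8, g=0: SD √0.4 = 0.632, and 0/0.632 = 0. There is a strong association and nothing for the test to detect.
- ρ=0, g=1: SD √2 = 1.414, and 1/1.414 = 0.707. There is no association and a large apparent effect.
- ρ=−0.8, g=1: SD √3.6 = 1.897, and 1/1.897 = 0.527. The association runs against the hypothesis and there is still a sizeable effect.

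When g is zero, ρ drops out. When g is not zero, ρ only rescales the gap.

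**Simulation.** Bivariate normal data, n=15 (from Section 10.5), two-sided 0.05, 20,000 runs per cell. Gaps and correlations are assumptions, because the documents give none. Signed-rank rejection rates:

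| Correlation | gap 0 | 0.5 SD | 1 SD | 3 SD |
|---|---|---|---|---|
| −0.8 | 4.9% | 14.6% | 45.4% | 100% |
| 0 | 4.6% | 23.6% | 69.7% | 100% |
| 0.8 | 5.0% | 78.9% | 100% | 100% |

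Spearman's test rejects in about 5% of runs at correlation 0 and about 94% at −0.8 or 0.8, at every gap. At a 3 SD gap, signed-rank gives the same answer for a strong positive, a strong negative and no association.

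**Active treatment versus BCI alone.** Therapy in the past 30 days is an attribute of the participant, so membership of the two groups does not overlap. A within-group signed-rank test has the null hypothesis of no change in that group. The question in item 2 has the null hypothesis of equal change in the two groups. If both groups change by the same 0.75 SD, so that there is no enhancement, signed-rank within a group still rejects in about 37% of runs with 7 participants and 60% with 12 (group sizes assumed). Those rejections are correct for change within the group and say nothing about enhancement.

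**The case against.** The strongest reply is that little depends on this. Section 10.4.1 says the secondary outcomes are not powered, Section 10.5 says the sample cannot settle the immune endpoint, and Section 4.2.3 places the active-treatment question among the exploratory endpoints. The better tests will be imprecise too. An observed rho of 0.5 has an approximate 95% CI of −0.05 to 0.82 at n=15 and −0.36 to 0.90 at n=8. Rank-sum power for a 0.75 SD difference in change is about 18% to 38% over assumed splits from 3 and 12 to 12 and 12. All of this stands. It limits the consequence but does not make signed-rank answer the question, and hypothesis 3 is one of the three hypotheses the plan lists.

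A second reply is that Section 10.4.7 refers back to Section 10.4.4, where the test is used on pre/post pairs, so the natural reading is a pre/post test within each subgroup. That is fair. The defect there is that the between-group test is missing.

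A reader might infer three stronger points, which the documents do not support:
- That the plan will test each group separately and compare the two significance results, with a calculable false-signal rate. The plan states no such procedure and gives no group sizes, so any such rate would mostly reflect the power of the within-group tests.
- That the dose-level analyses in Section 10.4.7 item 1 are also wrong. They use genuine pre/post pairs, and Section 4.2.3 labels the freeze-time aim exploratory.
- That the simulated percentages estimate an error rate in this trial. They illustrate how the test behaves on assumed scales.

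**Conclusion.** The point holds for two analyses. For hypothesis 3, the assigned test does not address the stated endpoint. It can miss a strong association (about 5% rejection at correlation 0.8 with no gap) or reject with none present (about 70% at a 1 SD gap). The percentages rest on normal data, n=15 and assumed scales, but the mismatch does not, because it follows from what the test is. For active treatment versus BCI alone, the plan poses a between-group contrast and names no test that can assess it.

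Signed-rank remains suitable for pre/post blood. The feasibility, DLT and MTD analyses are unaffected. This should be fixed before the immune data are analysed, and it is not a reason to doubt the primary results.

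**What to change.** **Section 10.4.4.** Keep signed-rank for pre versus post blood. For hypothesis 3, specify Spearman's rho with a 95% CI between the pre-BCI BAL PD-1+ percentage and the change in the CD8 marker at one pre-specified post-BCI day, and report the number of participants with usable BAL. A rank-sum test of that change between high and low PD-1 would also serve, if the cut-off is set in advance.

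**Section 4.2.2.** Align the responder-category comparison with that choice, so that the correlation, high-PD-1 and responder framings become one analysis. If the responder comparison is kept separately, define a responder and name its test.

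**Section 10.4.7 item 2.** Specify a Wilcoxon rank-sum test on change scores between the two groups, with an estimate of the difference and its CI, and report both group sizes.

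**Cost.** A wording amendment, which Section 13.2 requires the IRB to approve before it takes effect, and a few lines of code. No new participants, samples or assays are needed.

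### The signed-rank test planned for hypothesis 3 cannot test it, and a correlation run on post-BCI levels could pass a stable personal trait off as response; use the log post/pre ratio

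*Combined protocol and SAP*

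**What the plan says.** Section 10.2 states the third hypothesis: "CD8+ T cell responses to BCI will be greater among subjects with high PD-1 expressing T cells in BAL effluent". Section 3.2 repeats it in similar terms.

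Three places bear on how it is to be analysed, and they differ.

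- **Section 10.4.4**, the only statistical method given, first says that "Wilcoxon signed-rank tests will be used to assess paired pre- and post-BCI peripheral blood measurements". The same sentence then applies the same test to paired post-BCI blood CD8+ "T cell responses and T cell PD-1 expression in BAL effluent".
- **The Protocol Summary** lists the endpoint as "Correlation of PD-1 phenotype of pre-BCI BAL lymphocytes by single-cell RNA sequencing and BCI-induced anti-tumor immune responses".
- **Section 4.2.2** says that PD1+ "cell percentage and transcriptome will be compared between responder categories". It measures PD-1 in CD4+ and CD8+ "cells from both BAL and PBMC compartments", using only those participants with enough BAL material.

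The blood phenotype in section 10.2 is a combination of "Ki67⁺, PD-1+, HLA-DR⁺, CD38⁺, and Bcl-2^{low} compared to pre-BCI peripheral blood" CD8+ T cells, so PD-1 is one of the listed markers. Section 3.2 says only that some combination of these markers is expected. No section defines response, responder or high PD-1 for this hypothesis, or states a change score, ratio or baseline adjustment for it. Blood is drawn on day 0 before BCI (section 4.2.2), and there is no control group (section 6.1.1).

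**The concern.** There are two linked problems.

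First, a signed-rank test on pairs of blood response and BAL PD-1 asks whether one quantity tends to exceed the other. Hypothesis 3 asks whether people with more of one have more of the other. The test does not answer that question.

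Second, replacing the test is not enough. Within one sentence, section 10.4.4 refers to pre- and post-BCI values for the blood comparison but only to post-BCI values for the BAL comparison. If the Protocol Summary's correlation, or the responder comparison of section 4.2.2, is run on post-BCI levels, a person whose T cells are activated or PD-1-rich in both compartments before any freezing scores high on both axes. PD-1 may also be a component of both variables. Without a control group, nothing else in the design separates such a trait from an effect of BCI.

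At stake is a secondary finding. Section 10.4.1 sets significance at 0.05, and section 10.5 intends the results to inform later studies of BCI with anti-PD-1 therapy.

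**Working it through.** **The plan's own figure.** Section 10.5 gives about 80% power with 15 subjects, a difference of 0.75 SD and a within-subject correlation of 0.5. The SD of the difference is SD × √(2 × (1 − 0.5)) = SD, so the standardised effect is 0.75. The normal approximation at two-sided 0.05 gives Φ(0.75 × √15 − 1.96) = Φ(0.945) = 82.8%. The t-test gives 77.1% and a simulated signed-rank test 74.9%. The figure is reproduced as a rough value. It covers the pre/post blood comparison only; no figure is given for hypothesis 3.

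**The test as written.** Simulated rejection rates at n = 15, two-sided 0.05:

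| Gap in mean level | BAL-blood correlation 0 | 0.5 | 0.7 |
|---|---|---|---|
| none | 4.5% | 4.9% | 4.5% |
| 1 SD | 69% | 94% | 99% |
| 2 SD | >99% | >99% | >99% |

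With equal levels the test does not respond to association at all. With unequal levels it rejects even when there is no association.

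**An association test in its place.** Inputs:

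- Within-subject correlation between pre- and post-BCI blood: 0.5 (section 10.5).
- Two-sided level 0.05. Section 10.4.1 gives 0.05; two-sided is an assumption.
- n = 20, an assumption inside the range of 15 to 24 in section 5.6. The size of the BAL subset is not stated.
- Log-normal blood phenotype with log SD 0.7 (assumption).
- Correlation *r* of BAL PD-1 with log blood phenotype, equal before and after BCI. The documents give no value, so 0, 0.3, 0.5 and 0.65 are shown.
- No link between BAL PD-1 and the effect of BCI, so every significant result is false.

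Share of simulated trials significant (Spearman; simulation error about 1 to 2 points):

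| Response variable | r = 0 | 0.3 | 0.5 | 0.65 |
|---|---|---|---|---|
| Post-BCI level, no BCI effect | 5% | 22% | 58% | 86% |
| Raw change, the same 3-fold rise in everyone | 5% | 13% | 29% | 47% |
| Log post/pre ratio | 5% | 5% | 5% | 5% |
| Log ratio, adjusted for the pre-BCI value | 5% | 10% | 23% | 45% |

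For the post-BCI level, n = 15 gives about 5% / 18% / 44% / 72%, and n = 24 about 5% / 27% / 66% / 92%.

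**Why the rows differ.**

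- *Log ratio.* On the standardised log scale its correlation with BAL PD-1 is (r_post − r_pre) / √(2 × (1 − 0.5)) = r_post − r_pre. This is zero when the two are equal.
- *Raw change.* A common fold rise adds more percentage points to those who start higher, so the trait stays in the difference.
- *Adjusted analysis.* The partial correlation is (r − 0.5r) / √((1 − 0.5²)(1 − r²)). At r = 0.5 this is 0.25 / 0.75 = 0.33, not zero, because one noisy baseline captures only part of the stable trait.

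**The case against.** **Does the written analysis itself create the bias?** A reader might infer that section 10.4.4, as it stands, makes people with high PD-1 look like greater responders. It does not: the signed-rank test is blind to association. The bias arises only when that test is replaced by the correlation or group comparison named elsewhere and run on post-BCI levels.

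**Did the plan decide against a baseline?** A reader might also infer this, and the documents do not support it. Section 10.2 speaks of responses to BCI, and the Protocol Summary speaks of changes and of BCI-induced responses. A change-from-baseline reading is open. What stands is that section 10.4.4 does not state one, and that a raw percentage-point change would still carry part of the bias.

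**Is PD-1 certainly in both variables?** No. The blood phenotype is not fixed. The trait problem does not need it, since any stable trait linked to BAL PD-1 behaves in the same way.

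**Is the size known?** No. At a BAL-blood correlation of zero there is no bias. But both measurements concern T cells of the same person, so zero should not be presumed.

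**Does it matter in an unpowered secondary aim?** Section 10.4.1 says that the study is not powered for secondary outcomes, which limits the stakes. It does not make a test suitable that cannot address its hypothesis.

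**Conclusion.** The concern holds in this form: the test in section 10.4.4 cannot address hypothesis 3, and the natural replacement, run on post-BCI levels, can report a stable trait as a response to BCI. With 20 participants and no BCI effect, the false-positive rate runs from 5% at a BAL-blood correlation of 0 to about 86% at 0.65. That correlation is assumed, so the range is the result, not any single value in it.

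The remedy's 5% rests on BAL PD-1 relating equally to log pre- and log post-BCI blood. If it tracks the same-day pre-BCI sample more closely, the log ratio is biased against the hypothesis. For example, correlations of 0.5 before and 0.4 after give 0.4 − 0.5 = −0.1.

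Adjusting for the pre-BCI value looks like the usual cure, but under the stable-trait model it brings the artefact back.

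**What to change.** In section 10.4.4, for hypothesis 3:

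1. Replace the signed-rank test by a Spearman correlation between continuous BAL PD-1 and response.
2. Define response as the log post/pre ratio of the blood CD8+ phenotype, using the day-0 sample. State the exact marker combination, the post-BCI day (7 or 14), the BAL site (two are sampled) and a rule for zero frequencies.
3. Do not adjust for the pre-BCI value. State the equal-correlation assumption.
4. As a sensitivity analysis, repeat with a phenotype that leaves PD-1 out: Ki67+, HLA-DR+, CD38+, Bcl-2 low. All four markers are in Panel 2 of the table in section 2.1.
5. Use the same definition of response for the responder categories in section 4.2.2, and report how many participants have both BAL and paired blood data.

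The cost is wording only; the samples and markers are already planned. The ratio is noisier than a single level, and with only a subset contributing BAL data the result should be labelled exploratory. The signed-rank test can stay for the pre/post blood comparison.
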